8.2.3. Missing Doses

All efforts should be made to administer IP on all of the scheduled days of each 28-day treatment cycle. Any missed doses of CC-486 during that period should not be taken after the last scheduled day of administration, but should be returned by the subject for IP accountability.

8.2.4. Dose Modifications and Toxicity Management

8.2.4.1. CC-486 (Oral Azacitidine) Dose Modification and Toxicity Management

All efforts should be made to maintain treatment with CC-486 according to schedule without cycle delay, dose interruption, or reduction. Subjects will be monitored for hematologic toxicity and non-hematologic toxicity with the NCI CTCAE Version 4.03 used as a guide for the grading of severity.

If adverse events are observed that are considered by the investigator to be at least possibly related to treatment, CC-486 dosing may be interrupted, delayed or modified. The investigator is encouraged to contact the medical monitor prior to any treatment adjustment, if possible.

For any adverse event that would put a subject at unacceptable risk in the investigator's opinion (eg, Grade 4 neutropenia), CC-486 dosing may be interrupted, delayed or modified, even if not considered by the investigator to be at least possibly related to treatment.

A minimum CC-486 dose and schedule of 100 mg BID 14/28d (or 200 mg QD 14/28d) is permitted in the event of toxicity (see [Table 3](#)). Subjects who cannot tolerate this minimum dose and schedule should discontinue the treatment phase of the study and enter follow-up.

Subjects who have their CC-486 dose reduced or treatment schedule modified may return to their original dose and/or schedule in a stepwise fashion upon discussion and documented agreement between the investigator and the medical monitor, provided that at least two treatment cycles have proven tolerable at the current dose and schedule. The treatment schedule should first be increased from 14/28 days to 21/28 days at 100 mg BID (or 200 mg QD if the rescue dosing option was utilized), followed by a stepwise escalation in dose (eg, 100 mg BID to 150 mg BID or 200 mg QD to 300 mg QD, etc.). At least two treatment cycles without unacceptable drug-related toxicity should precede any increase in dose or schedule.

In the absence of unacceptable toxicity, subjects who show signs of worsening disease (clinical or hematological), who remain in stable disease, or do not experience modified IWG 2006 hematologic improvement (HI) or better (PR, CR or marrow CR – modified IWG 2006, [Appendix F](#)) after 2 well-tolerated cycles, may have their **dose increased** at the discretion of the investigator and in discussion with the medical monitor as described in [Section 6.5](#) and [Table 3](#). Again, dose and schedule may be adjusted as described in [Section 8.2.4](#) in order to manage toxicity.

After Amendment 4 approval, dose increases will no longer be allowed. Dose decreases following Table 3 are still allowed. Subjects will continue at the same dose levels during the Extension Phase. Any potential dose escalation will be considered a treatment failure and the subject should be discontinued.

Refer to Section 8.2.5 if, despite temporary interruption, delay or modification of study treatment, the toxicity persists for more than 42 days and is considered by the investigator to be at least possibly related to study treatment.

Following any modification of study treatment or if a dose is missed, the subject should stay on the visit schedule as specified in Table 2. Unscheduled visits may occur to monitor the subject's toxicities if necessary.

Table 3: CC-486 Dose Modification Steps

Dose Modification Step	BID Dose and Schedule Days	Rescue Step	Rescue (QD) Dose and Schedule (Days)
+2	300 mg BID, 21/28		
+1	250 mg BID, 21/28		
0 ^a	200 mg BID, 21/28		
-1	150 mg BID, 21/28	R+2	300 mg QD, 21/28
-2	100 mg BID, 21/28	R+1	200 mg QD, 21/28
-3 ^b	100 mg BID, 14/28	Rescue (R)	200 mg QD, 14/28

BID = twice daily; QD = once daily; R = rescue dose step.

^a Highest starting dose to be evaluated.

^b Any subject who cannot tolerate dose modification Step -3 (or R) will discontinue IP and enter the follow-up period.

→ Dose adjustment options from current dose/regimen. Dose/schedule reduction does not need to be taken stepwise.

Dose Modification for Febrile Neutropenia

Any subject who experiences febrile neutropenia \geq Grade 3 that persists for up to 3 days may, with concomitant antibiotic, antiviral, and/or antifungal therapy, continue to receive IP uninterrupted at the investigator's discretion. If the event exceeds 3 days, IP should be temporarily interrupted. Dose modification may be considered as summarized in Table 4.

Dose Modification for Neutropenia Grade 4

For subjects entering the study with pre-existing Neutropenia Grade 4, treatment should be started at the regular starting dose and schedule of 200 mg BID 21/28d. However, if neutropenia continues to worsen under treatment, dose modification may be considered as summarized in Table 4.

For any subject who experiences a worsening of neutropenia to Grade 4 for ≥ 4 days, independent of whether considered related to IP or not, a dose modification may be considered as summarized in [Table 4](#).

Dose Modification for Diarrhea

It is recommended that subjects experiencing diarrhea be managed according to the guidelines provided in [Appendix H](#). Anti-diarrhea medication may be administered as prophylaxis against diarrhea and for treatment of any adverse events of diarrhea. Recommended dose modification steps for diarrhea (\geq Grade 2) are summarized in [Table 4](#). If further dose-reduction beyond modification Step -3 (or the QD *rescue* regimen) is thought to be necessary, IP should be discontinued and the treatment discontinuation visit scheduled.

Dose Modification for Nausea and Vomiting

A serotonin (5-HT₃) receptor antagonist (eg, ondansetron) or other comparable medication may be administered as an antiemetic prophylaxis approximately 30 minutes prior to IP administration if necessary. Antiemetic pretreatment is recommended during the first cycle of the treatment phase. If the subject does not experience significant nausea and/or vomiting, further use of antiemetic medications may not be necessary. Antiemetic medication(s) should be administered for treatment of any adverse events of nausea and/or vomiting. Recommended dose modifications for nausea and vomiting (\geq Grade 3) are summarized in [Table 4](#). If further dose-reduction beyond modification Step -3 (or the QD *rescue* regimen) is thought to be necessary, IP should be discontinued and the treatment discontinuation visit scheduled.

Dose Modification for Renal Dysfunction and Abnormal Serum Electrolytes

If unexplained elevations of serum creatinine or electrolyte disturbances occur, dose or schedule modifications may be implemented as summarized in [Table 4](#). If further dose-reduction beyond modification Step -3 (or the QD *rescue* regimen) is thought to be necessary, IP should be discontinued and the treatment discontinuation visit scheduled.

Dose Modification for Weight Change

No dose adjustment should be made for weight loss or gain alone; however, the reason for weight loss (eg, significant nausea, vomiting, anorexia, etc.) or weight gain (eg, peripheral edema) should be investigated and may require a dose modification as specified in [Table 4](#).

Dose Modification for Any Other Adverse Event

Any subject who experiences any hematologic or non-hematologic adverse event \geq Grade 2, that is a worsening from baseline state (see [Section 6.4](#) for baseline definition) and would put a subject at unacceptable risk in the investigator's opinion, may have IP dosing temporarily interrupted until the adverse event returns to \leq Grade 1 or baseline state. This decision is not dependent on the relationship between the AE and IP (related or not). Recommended dose modifications for *other* \geq Grade 2 hematologic or non-hematologic adverse events are summarized in [Table 4](#).

Table 4: Guidelines for CC-486 Toxicity Management and Dose Modifications

NCI CTCAE Toxicity Grade	Action

Febrile Neutropenia (≥ Grade 3)
	
 • Continue IP at the discretion of the investigator 
 – If episode persists for ≥ 4 days despite adequate/maximal antibiotic, antiviral and/or antifungal therapy, IP should be temporarily interrupted. – Resume IP at the same dose after the fever has resolved and the ANC has improved or stabilized (as assessed by the investigator). IP should not be resumed for at least 3 days following resolution of fever. Guidance for the use of growth factors and prophylactic antibiotics is provided in Section 9.1. • If a subject experiences febrile neutropenia in 2 consecutive cycles, the steps noted above should be followed, but the IP dose should be reduced by at least 1 step upon resumption of treatment with IP. Secondary prophylaxis with G-CSF may be considered. 
If subject continues to experience febrile neutropenia episodes that are deemed to be related to IP by the investigator, the dose and schedule may be modified further according to Table 3.


Neutropenia Grade 4 (related or unrelated to IP)
	
Pre-existing Neutropenia Grade 4
 
 • Continue IP at the discretion of the investigator 
 – If the neutropenia continues to worsen significantly under treatment in the investigator’s opinion, treatment may be temporarily interrupted. – Resume IP after the ANC has improved or stabilized (as assessed by the investigator). IP dose/schedule may be reduced at the investigator’s discretion (see Table 3). • If the subject continues to experience Grade 4 neutropenia during 2 consecutive cycles, IP dose/regimen should be reduced by at least 1 step (Table 3). Secondary prophylaxis with G-CSF may be considered. 
Subjects experiencing worsening of Neutropenia to Grade 4 during IP treatment
 
 • Continue IP at the discretion of the investigator 
 – If episode persists for ≥ 4 days, IP may be temporarily interrupted. – Resume IP after the ANC has improved or stabilized (as assessed by the investigator). IP dose/schedule may be reduced at the investigator’s discretion (see Table 3). • If the subject continues to experience Grade 4 neutropenia during 2 consecutive cycles, IP dose/regimen should be reduced by at least 1 step (Table 3). Secondary prophylaxis with G-CSF may be considered.

Diarrhea (≥ Grade 2)
	
 • Interrupt IP and provide adequate/maximum medical intervention • Resume IP at same dose when toxicity resolves to ≤ Grade 1 • If event reoccurs upon re-challenge or during the subsequent treatment cycle, modify IP dose/schedule by at least 1 step according to Table 3.

**Table 4: Guidelines for CC-486 Toxicity Management and Dose Modifications
 (Continued)**

NCI CTCAE Toxicity Grade	Action
Nausea and/or Vomiting (≥ Grade 3)	
 • Interrupt IP and provide adequate/maximal medical intervention • Resume IP at same dose when toxicity resolves to ≤ Grade 1 • If event reoccurs upon re-challenge or during the subsequent treatment cycle, modify IP dose/schedule by at least 1 step according to Table 3.
Renal Dysfunction	
 • For unexplained elevations of serum creatinine, delay the start of the next cycle of treatment until values return to baseline. Reduce IP dose in the next cycle of treatment by at least 1 step. • The treatment dose and/or schedule can be reduced per Table 3 if the elevation of serum creatinine recurs in the subsequent cycle. • Discontinue IP if similar unexplained renal and/or electrolyte disturbances subsequently persist or recur during the next cycle of treatment.
Other ≥ Grade 2 AEs	
 • Consider interrupting IP and provide medical intervention as appropriate • Resume IP at same dose when toxicity resolves to ≤ Grade 1 • If event reoccurs upon re-challenge or at same intensity during next treatment cycle, modify IP dose/schedule according to Table 3.

Abbreviations: AE = Adverse Event; ANC = Absolute Neutrophil Count; CTCAE = Common Terminology Criteria for Adverse Events; G-CSF = granulocyte colony-stimulating factor; IP = Investigational Product; NCI = National Cancer Institute.

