Subjects will undergo screening procedures over a period of up to 28 days following the signing of their informed consent document (ICD). Eligible subjects will continue to the safety run-in or the randomized treatment phase of the study where they will receive IP for up to six 28-day treatment cycles. Those who derive benefit from the treatment may continue IP until loss of that benefit (Section 4.1.3).

After treatment discontinuation, subjects will be followed for 28 days for CC-486 safety-related issues and 90 days for durvalumab safety-related issues. After that, subjects will be contacted by telephone every 3 months in the follow-up phase of the study.

The enrollment period for this study is expected to last approximately 39 months. The treatment and follow-up periods are expected to conclude approximately 12 months after the last subject is enrolled. The Extension Phase is expected to last approximately 24 months. Therefore, the total duration of the study is expected to be approximately 75 months.

The *End of Trial* is defined as either the date of the last visit of the last subject to complete the study, or the date of receipt of the last data point from the last subject that is required for primary, secondary and/or exploratory analysis, as pre-specified in the protocol and/or the Statistical Analysis Plan (SAP), whichever is the later date.

The study will conclude once all subjects have completed or discontinued from the Extension Phase.

Study Treatment (Investigational Product – IP)

CC-486 (Oral Azacitidine)

Eligible subjects who are assigned to the monotherapy treatment arm will receive CC-486 at the dose and schedule identified during the safety run-in phase of the study. Dose and schedule may be reduced to manage toxicity or increased as described in Section 8.2. Subjects can continue treatment with CC-486 as long as all protocol-specified re-treatment criteria continue to be met (see Section 8.2.5).

Durvalumab (MEDI4736)

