4.1.2. Safety Run-in

The safety run-in will utilize a conventional 3+3 design to find a tolerable dose for the randomized treatment phase. The subjects will be treated with CC-486 first to confirm the expected safety profile of CC-486 alone at the planned dose and schedule in the target population. The maximum administered dose (MAD) of CC-486 will not exceed 300 mg BID (21/28 days). The resulting tolerable dose of CC-486 will then be used to combine with durvalumab 1500 mg for the combination therapy.

The completion of the CC-486 safety run-in has determined 100 mg BID, 21/28 day regimen (dose level -2) as the CC-486 dose to proceed into the combination therapy safety run-in.

The dose-finding procedure for CC-486 and CC-486+durvalumab will proceed as following.

Part (A) - starting dose for CC-486 as monotherapy: A group of 3 subjects will receive CC-486 at dose level 0 (200 mg BID (21/28 days) and will be closely monitored through at least 2 treatment cycles for dose-limiting toxicities, as defined in Section 4.1.2.1. If for any reason the monotherapy safety run-in starting dose needs to be reduced, the starting dose will follow the established levels in [Table 1](#).

1. If #Subject with DLT = 0/3, the dose will be declared tolerable and used as the starting CC-486 dose.
2. If #Subject with DLT = 1/3, recruit another 3 subjects to test the same dose.
 - a. If #Subject with DLT = 1/6, the dose will be declared tolerable and used as the starting CC-486 dose.
 - b. If #Subject with DLT \geq 2/6, the dose will be declared intolerable and the next lower dose level of CC-486 according to [Table 1](#) will then be explored. Repeat the entire procedure with 3 new subjects.
3. If #Subject with DLT \geq 2/3, the dose will be declared intolerable and the next lower dose level of CC-486 according to [Table 1](#) will then be explored. Repeat the entire procedure with 3 new subjects.

The safety run-in for CC-486 monotherapy has been completed as of December 2016.

Part (B) - starting dose for CC-486+durvalumab as combination therapy: A group of 3 subjects will receive CC-486 dose determined in Part (A) above plus durvalumab 1500 mg (given by IV infusion [over 1 hour \pm 5 minutes] on Day 1 of each 28-day treatment cycle) and will be closely monitored through at least 2 treatment cycles for dose-limiting toxicities, as defined in Section 4.1.2.1.

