6.5. CC-486 (Oral Azacitidine)

All eligible subjects will receive treatment with CC-486 at the dose and schedule identified during the safety run-in. Dose and schedule may be decreased as described in Section 8.2.4 in order to manage toxicity. In the absence of unacceptable toxicity, subjects who show signs of worsening

disease (clinical or hematological), who remain in stable disease, or do not experience modified IWG 2006 hematologic improvement (HI) or better (PR, CR or marrow CR – modified IWG 2006, [Appendix F](#)) after 2 well-tolerated cycles, may have their **dose increased** at the discretion of the investigator and in discussion with the medical monitor as defined in [Table 3](#). Again, dose and schedule may be adjusted as described in [Section 8.2.4](#) in order to manage toxicity.

After at least 2 treatment cycles at the increased dose, the assigned dose can be further increased if it is well-tolerated but no objective response is observed.

Special attention should always be given to potential drug-related toxicity and/or tolerability issues so dose and/or schedule can be reduced appropriately ([Section 8.2.4](#)).

Subjects can continue treatment with CC-486 as long as all protocol-specified re-treatment criteria continue to be met (see [Section 8.2.5](#)).

Best supportive care should be used in combination with study treatment as deemed necessary. Best supportive care includes, but is not limited to, treatment with RBC transfusions (pRBC or whole blood), single donor or pooled donor platelet transfusions, antibiotic, antiviral and/or antifungal therapy, antiemetic and/or antidiarrheal support, nutritional support as needed, and granulocyte (or granulocyte macrophage) colony-stimulating factors for subjects experiencing neutropenic fever or infection, and may be given as secondary prophylaxis ([Section 9.1](#)). Best supportive care for this study excludes the use of ESAs and other hematopoietic growth factors, except as noted for G- or GM-CSF in [Section 9.1](#). It is recommended that an antiemetic medication such as ondansetron or an appropriate locally-available equivalent be taken 30 minutes prior to CC-486 administration during Cycle 1 of the treatment phase. If nausea/vomiting is not significant, further antiemetic prophylaxis may not be needed.

Refer to [Section 8.2](#) for details regarding IP dispensation, administration, and accountability.

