8.2. Treatment Administration and Schedule

After the safety run-in is complete and the CC-486 dose and regimen to be used in combination with durvalumab is established, eligible subjects will be randomized to receive CC-486 alone or in combination with durvalumab in the randomized treatment phase of the study. All randomized subjects will receive CC-486 orally administered tablets at the established dose and schedule. The schedule will include BID dosing on days 1-21 of each 28-day treatment cycle. Subjects randomized to the combination therapy arm will receive durvalumab, 1500 mg on Day 1 of each 28-day treatment cycle by IV infusion over approximately 1 hour (\pm 5 minutes). CC-486 tablets should be ingested approximately 1 hour after completion of the durvalumab infusion on Day 1 of each treatment cycle (except for Cycle 1 in which CC-486 is given on Day -1 for PK sub-study subjects) as described in Section 8.2.2. In the event of unacceptable toxicity, CC-486 dose and schedule may be modified (see Section 8.2.4). Infusions of durvalumab may be interrupted, slowed, or discontinued in order to address toxicity, but dose reduction of durvalumab is not permitted (see Section 8.2.4.2).

In the absence of unacceptable toxicity, subjects who show signs of worsening disease (clinical or hematological), who remain in stable disease, or do not experience modified IWG 2006 hematologic improvement (HI) or better (PR, CR or marrow CR – modified IWG 2006, [Appendix F](#)) after 2 well-tolerated cycles, may have their **dose increased** at the discretion of the investigator and in discussion with the medical monitor as described in Section 8.2.4 and [Table 3](#). Again, dose and schedule may be adjusted as described in Section 8.2.4 in order to manage toxicity.

Subjects may continue to receive the protocol-prescribed therapy for as long as they benefit from the treatment (Section 4.1.3) or until treatment is discontinued for reasons detailed in Section 12.

Prior to discontinuing a subject, it is recommended that the investigator contact the medical monitor and forward appropriate supporting documents for review and discussion. However, the decision to discontinue a subject remains the responsibility of the treating physician and will not be delayed or refused by the sponsor.

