- Updated to include a timeframe for availability for documentation. If documentation of myelodysplastic syndrome (MDS) diagnosis, World Health Organization (WHO)/French-American-British (FAB) classification and International Prognostic Scoring System (IPSS)/IPSS-Revised (-R) risk categorization is available “and within 2 months of screening”, results of central review are not required prior to enrollment of the subject in the study.

Revised sections: Section 4.1.1. Screening Phase, Table 2 Table of Events, and Section 6.1.15 Bone Marrow Aspirate, Biopsy, and Peripheral Blood Smear.

- Based on the outcome of the CC-486 safety run-in, the CC-486 starting dose was lowered from 200 mg BID, 21/28 day to 100 mg BID, 21/28 day for the combination safety run-in therapy and the Phase 2 CC-486 monotherapy.

The dose levels in Table 1 were updated to “0 to -3” instead of specifically noting a “starting dose” of 200 mg BID, 21/28 only.

Also, clarification is added to state that the safety run-in for CC-486 monotherapy has been completed as of December 2016.

Revised sections: Sections 4.1.2 Safety Run-in, Table 1: CC-486 Dose Levels for Safety run-in, and Table 3: Dose Modification Steps.

- Updated text to include “Please refer to Section 4.1.2.1 for CC-486 related dose-limiting toxicity criteria”. Criteria was defined for durvalumab dose-limiting toxicities and wanted to guide the reader to the previous section for CC-486 specific dose-limiting toxicities (for their reference) as this is combination therapy investigating both CC-486 + durvalumab.

Revised section: Section 4.1.2.2 Durvalumab/CC-486 Combination Therapy Dose-Limiting Toxicity.

- Additional sample collections are allowed if the site would like to work-up the subject for progression. Footnote p was updated to include that unscheduled sample collections are also permitted if disease progression is suspected.

Revised section: Table 2: Table of Events

- The window for inclusion criterion number 5 which was originally 12 weeks was increased to 16 weeks due to the difficulty for sites to gather prior subject data with regard to prior transfusions, prior iHMA treatments, etc. which potentially would come from outside hospitals or other treating institutions. Alignment was gained with the Study Steering Committee to extend this window from 12 to 16 weeks.

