8. STUDY TREATMENTS AND EXTENT OF EXPOSURE

Following variables regarding the extent of study drug exposure are defined and will be summarized.

- ***Treatment Duration:***
 - Definition: (study treatment end date – first study drug start date + 1)/30.4167.
 - Descriptive summary statistics will be provided. An additional table will be created for all treated subjects, displaying number of subjects by cycle. A by-subject listing of all exposure information collected on the CRF will be provided.
- ***Number of Treatment Cycles:***
 - Descriptive summary statistics will be provided for safety population.
- ***Duration of exposure:***
 - Definition: total number of days on the study drug during the treatment period (excluding the periods of dose break per protocol or dose interruptions).
 - Descriptive summary statistics will be provided for safety population.
- ***Average Length of Cycle:***
 - Definition: the number of days on treatment divided by the number of cycles.
 - Descriptive summary statistics will be provided for safety population.
- ***Average Number of Days Dosed Per Cycle:***
 - Definition: the number of days a subject is dosed divided by the number of cycles the subject had.
 - Descriptive summary statistics will be provided for safety population.
- ***Cumulative Dose:***
 - Definition: the sum of all doses taken during the treatment period (in milligrams).
 - Descriptive summary statistics will be provided for safety population by cohort and overall.
- ***Average Daily Dose:***
 - Definition: the cumulative dose of the study drug divided by the number of days dosed (received a non-zero dose).
 - Descriptive summary statistics will be provided for safety population.
- ***Dose Intensity:***

- Definition: the cumulative dose of the study drug divided by treatment duration of the study drug.
- Descriptive summary statistics will be provided for safety population.
- ***Dose Modification:***
 - Descriptive summary statistics will be provided for safety population, including
 - subjects who have at least one dose reduction/interruption,
 - time to first dose reduction/interruption,
 - first dose reduction/interruption due to AE,
 - duration of first dose reduction/interruption due to AE.

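### Protocol Section 8.2.4.1 still gives 200 mg BID as the regular CC-486 starting dose for subjects with pre-existing Grade 4 neutropenia, twice the dose set by the run-in

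*Protocol*

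**What the plan says.** The paragraph on Grade 4 neutropenia in Protocol Section 8.2.4.1 covers subjects who already have Grade 4 neutropenia at entry. For them, "treatment should be started at the regular starting dose and schedule of 200 mg BID 21/28d". It then allows dose modification if the neutropenia worsens on treatment.

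Other parts of the current protocol bear on the starting dose:

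- **Section 4.1.2:** completion of the CC-486 run-in "has determined 100 mg BID, 21/28 day regimen (dose level -2) as the CC-486 dose to proceed into the combination therapy safety run-in".
- **Protocol Summary, Study Treatment:** subjects assigned to monotherapy "will receive CC-486 at the dose and schedule identified during the safety run-in phase of the study".
- **Section 6.5:** "All eligible subjects will receive treatment with CC-486 at the dose and schedule identified during the safety run-in".
- **Section 8.2:** "All randomized subjects will receive CC-486 orally administered tablets at the established dose and schedule".
- **Table 3, footnote a:** 200 mg BID (Step 0) is described as the "Highest starting dose to be evaluated".

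The justification for the amendment that changed the dose says it was lowered from 200 mg BID "to 100 mg BID, 21/28 day for the combination safety run-in therapy and the Phase 2 CC-486 monotherapy". That text is used here only as corroboration.

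On exposure, SAP Section 8 states: "A by-subject listing of all exposure information collected on the CRF will be provided".

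**The concern.** The sentence sets no separate rule for neutropenic subjects. It says to start them on the regular dose without an up-front reduction, and then names a dose that stopped being the regular one when the run-in ended. Only the figure is wrong, but it is an explicit dose in the section that sites consult when neutropenia is the issue.

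Such subjects could enter. Section 7.3 sets an upper limit on white cell count but no minimum neutrophil count, and Table 4 has its own entry for pre-existing Grade 4 neutropenia. Before Amendment 4, Section 8.1.1 provided 100-, 150- and 200-mg tablets, so supply alone would not have prevented a 200 mg BID start.

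Two things are at stake: the safety of any subject started at twice the intended dose, and the accuracy of a report that presents Phase 2 exposure and safety as 100 mg BID data.

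**Working it through.** No sample-size, power or type I error formula applies. The check is a comparison of the dosing text, followed by simple arithmetic.

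**Step 1. Which dose does the protocol's own rule give?**

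- The Protocol Summary, Section 6.5 and Section 8.2 make the starting dose the one identified or established in the run-in. None makes an exception for neutropenia.
- Section 4.1.2 gives the run-in result as 100 mg BID 21/28, dose level -2. It names that dose for the combination run-in and does not itself name the Phase 2 monotherapy dose.
- Taken together, these put the Phase 2 starting dose at 100 mg BID 21/28. The amendment justification says the same outright.

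**Step 2. Can 200 mg BID be right on another reading?**

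- As level 0 of the run-in (Section 4.1.2, Table 1), it was the first dose to be tested. The sentence was therefore correct for the first run-in subjects, but not after the run-in settled two levels lower.
- As Step 0 of Table 3, it is labelled only as the top of the range of starting doses to be evaluated.

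Neither reading makes it the regular starting dose for Phase 2.

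**Step 3. Size of the discrepancy.** Daily dose = tablet dose × 2. Cycle dose = daily dose × 21 dosing days.

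| | Section 8.2.4.1 as written | Run-in dose |
|---|---|---|
| Daily dose | 200 × 2 = 400 mg | 100 × 2 = 200 mg |
| Dose per 28-day cycle | 400 × 21 = 8,400 mg | 200 × 21 = 4,200 mg |
| Table 3 step | 0 | -2 |

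Ratio: 8,400 / 4,200 = 2.0.

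**Step 4. How many subjects need checking?**

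- Planned for the two Phase 2 monotherapy cohorts: 2 × 16 = 32, plus any replacements.
- Ceiling: 65 enrolled (Section 4.1) less 13 in the monotherapy run-in (Amendment 4 justification) = 52. This ceiling also counts subjects from the combination run-in, so it overstates the Phase 2 group.
- Number actually started at 200 mg BID in Phase 2: not stated anywhere.

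**Step 5. Would the planned SAP tables show it?** SAP Section 8 summarises cumulative dose, average daily dose, dose intensity, and dose reductions or interruptions. None of these tabulates starting dose. Before Amendment 4, CC-486 could be increased after two well-tolerated cycles, so a raised average could reflect either a wrong start or a permitted increase. The by-subject listing can separate the two.

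**The case against.** The strongest reply is that the correction can no longer change a dosing decision. Enrolment is closed, the six ongoing subjects are past their starting dose, dose increases are barred after Amendment 4, and supply is now limited to 100-mg tablets. This stands, and it makes the point retrospective.

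Second, starting dose is governed by the Protocol Summary and Sections 6.5 and 8.2, which agree with one another, so a site could have resolved the stale figure. Drug allocation runs through the interactive response system, and the sponsor reviews documentation before enrolment. This lowers the risk, but the documents do not say that the system fixed the starting dose, and nothing shows that the figure was not followed.

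Third, exclusion criteria 17 and 18 let the investigator keep out subjects with hazardous laboratory abnormalities. Haematology is weekly in Cycles 1 and 2, and Table 4 provides for interruption and reduction. These are real safeguards, but they act around the figure and do not correct it.

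Fourth, the planned exposure listing and the deviation summary might reveal a 200 mg BID start anyway. The listing would contain it, but nobody is directed to look, and a site that followed the written sentence may not have recorded a deviation.

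Finally, 52 is a loose ceiling. That is accepted: the group of practical interest is the Phase 2 monotherapy cohorts, with 32 planned.

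**Conclusion.** The concern holds. Section 8.2.4.1 names a starting dose two-fold too high and two Table 3 steps above the dose set by the run-in, in current operative text. The conclusion rests on reading the Phase 2 dose as the run-in dose, which the Protocol Summary and Sections 6.5 and 8.2 require and the amendment justification confirms.

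The limits are clear. No document shows that any Phase 2 subject started at 200 mg BID, the number may be zero, and correcting the text protects no future subject. No effect on the Simon stopping rules, type I error, power or the response rate is claimed. It is still worth settling, because the contradiction concerns starting dose in a vulnerable subgroup and a negative answer is itself worth recording.

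**What to change.** In the Grade 4 neutropenia paragraph of Section 8.2.4.1, replace the 200 mg BID figure so that the starting dose and schedule read as those *identified during the safety run-in (100 mg BID 21/28d)*.

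Then filter the by-subject exposure listing in SAP Section 8 on first dose and flag every Phase 2 subject who started at 200 mg BID. For any subject found, report exposure and safety by actual starting dose. If there is none, state that in the report.

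The cost is one phrase in the protocol and one filter on a listing that is already planned.
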